6.4 Adverse Events

An adverse event (AE) is defined as any untoward medical occurrence (sign, symptom or abnormal laboratory finding) regardless of severity in a Subject or clinical-trial Subject administered a medicinal product and which does not necessarily have to have a causal relationship with this treatment. All adverse events, whether observed by an Investigator or Study Coordinator or reported by the Subject, whether related to study drug or not related to study drug, shall be documented on Subject records, together with details, i.e., date of onset,

description of the AE, the duration and intensity of each episode, the action taken, the relationship to the IMP and the degree of severity, the seriousness, date of resolution and the outcome.

All reported adverse events and serious adverse events will be recorded and reported as per section 11.0 Adverse Events.

6.5 COVID-19 symptom screening

Temperature check and COVID-19 symptom (such as Stuffy or runny nose, Sore throat, Shortness of breath (difficulty breathing), Cough, Low energy or tiredness, Muscle or body aches, Headache, Chills or shivering, feeling hot or feverish (temperature check), vomiting, diarrhea, loss of sense of taste and smell) screening will be done for each subject at visit 1, 2, 3, 4 and Unscheduled / Early Discontinuation visit. During the screening, if the subject found to have any one of the above said symptoms, then it will be judged by the investigator whether it is related or not-related to COVID-19 and appropriate procedures will be followed by the investigator and site¹⁰.

6.6 Lack of Treatment Effect (LOTE)

After completion of at least 4 weeks of the treatment period, if the subject comes to the Investigator and informs about not observing the desired treatment effect, then Investigator will evaluate the lesion counts and IGA scores and judge the lack of treatment effect. If the subject makes the decision to withdraw or discontinue from the study, then the reason for withdrawal/discontinuation will be coded as “lack of treatment effect (LOTE).”

7 CLINICAL EVALUATIONS

An examination of the Subject’s face will be performed at screening/baseline and at each subsequent visit. During the dermatologic examination, evaluations to determine efficacy of treatment will be conducted, including grading of the Subject’s facial acne using the criteria outlined in the IGA and lesion counts. **The IGA should be done before lesion counts.**

All Investigators or qualified staff who will perform evaluations of efficacy must attend study-specific training for the conduct of these evaluations (i.e., lesion counts and IGA).

7.1 Investigator's Global Assessment (IGA)

At each study visit, beginning at Visit 1, an Investigator will assess the overall status of the Subject's face for acne vulgaris using the IGA. To be included in the study, subjects must have a definite clinical diagnosis of acne vulgaris of severity grade 2, 3, or 4 at screening/baseline.

The following scale will be used for the IGA:

Grade	Definition
0	Clear skin with no inflammatory or non-inflammatory lesions
1	Almost clear; rare non-inflammatory lesions with no more than one small inflammatory lesion
2	Mild severity; greater than Grade 1; some non-inflammatory lesions with no more than a few inflammatory lesions (papules/pustules only, no nodular lesions)
3	Moderate severity; greater than Grade 2; up to many non-inflammatory lesions and may have some inflammatory lesions, but no more than one small nodular lesion
4*	Severe; greater than Grade 3; up to many non-inflammatory lesions and may have some inflammatory lesions, but no more than a few nodular lesions

* The eCRF will allow for reporting by Investigators of lesion worsening beyond Grade 4 with treatment. Subjects with nodulocystic acne vulgaris are not to be enrolled in the study. Subjects who worsen beyond Grade 4 will be described in the safety evaluation.

Please note that counts of nodules and cysts will be reported separately and not included in the inflammatory or non-inflammatory lesion counts.

7.2 Lesion Counts

At each study visit, beginning at Visit 1, an Investigator will assess by counting the number of open and closed comedones (non-inflammatory lesions), pustules and papules (inflammatory lesions) and nodulo-cystic lesions from the jaw line to the hairline. All lesions will be counted,

[REDACTED]

including those present on the nose. Counts of nodules and cysts should be reported separately and not included in the inflammatory or non-inflammatory lesion counts. A papule with a pustule on its apex will be counted as a pustule. [REDACTED]

[REDACTED]

To be included in the study, subjects must have ≥ 25 non-inflammatory lesions (i.e., open and closed comedones) AND ≥ 20 inflammatory lesions (i.e., papules and pustules) AND ≤ 2 nodulocystic lesions (i.e., nodules and cysts), at screening/baseline on the face.

Lesion Type	Definition
Closed Comedone	Non-inflammatory lesion; whitehead, skin-colored or slightly inflamed “bump” in the skin
Open Comedone	Non-inflammatory lesion: blackhead, surface of the plugged sebaceous follicle has a blackish appearance
Papule	Inflammatory lesion: a small (≤ 5 mm in diameter), solid palpable lesion, usually with inflamed elevation of the skin that does not contain pus
Pustule	Inflammatory lesion: a small (≤ 5 mm in diameter), inflamed skin swelling that is filled with pus
Nodules	Large, hard bumps under the skin's surface
Cysts	Similar to a nodule, but is pus-filled, and ≥ 5 mm in diameter

8 STUDY VISITS (SEE STUDY VISIT SCHEDULE)

8.1 Visit 1: Screening and Baseline (Day 0)

The following procedures will be performed at Visit 1:

1. **Written informed consent/assent will be obtained.** Subjects who are 18 years of age or older (up to the age of 40) must have provided IRB/IEC approved written informed consent. Subjects 12 to 17 years of age, inclusive, must have provided IRB/IEC approved written assent. Written assent must be accompanied by an IRB/IEC approved written informed consent from the Subject’s legally acceptable representative (i.e., parent or guardian). Prior to initiating screening for the study, Subjects will be given the approved ICF/informed assent form (IAF) describing the study and any risks associated with participation. The Subject will be allowed as much time as needed to read and understand the information presented in the consent/assent form. Appropriate study personnel will be available to answer any questions the Subject might have regarding the study or study-

related procedures. If the Subject chooses to participate in the study, he or she will be asked to sign and date the consent/assent form and will be provided with a copy for his or her records. Both the ICF and assent (if applicable) must be signed by the Subject or the Subject's legally acceptable representative (i.e., parent or guardian) before any protocol assessments can be undertaken.

2. **Screening/Baseline Demographics: Demographics** will be collected, including date of birth, gender, race and ethnicity.
3. **COVID-19** symptom screening.
4. **Medical History:** A complete medical history will be obtained for the Subject's current and past medical conditions. Significant medical history should include, but not be limited to, evidence of hypertension, lipid disorders, obesity*, heart attack, stroke, congestive heart failure, kidney disease, and auto immune disease and gestational diabetes. Significant surgical history should include, but not be limited to, removal of blockage from an artery and gallbladder removal.

* Obesity = BMI \geq 30 (as defined by Metropolitan Life Insurance Company Chart)

5. **Vitals:** Vital signs (blood pressure, pulse, respiratory rate and body temperature) will be documented. Subjects must remain in a seated position for at least 5 minutes before vital signs are obtained.
6. **Physical Examination:** A brief physical examination, including height (measured in inches) and weight (measured in pounds), will be performed. At a minimum, the physical examination will include the following: assessment of general appearance, skin, Head, Eyes, Ears, Nose and Throat (HEENT), heart, lungs, musculoskeletal system, lymph nodes, neurological systems, abdomen, and extremities.
7. **Concomitant Medications:** A complete list of current and past (within the previous 6-months) concomitant medications will be obtained for each Subject.
8. **Pregnancy Test:** A urine pregnancy test will be conducted for all females of childbearing potential.
9. **Clinical Assessment:** An evaluation of the patient's acne will be performed by an Investigator to determine the severity of the acne and confirm the diagnosis of acne vulgaris.
10. **Investigator Global Assessment:** The overall status of the Subject's facial acne vulgaris (from the jaw line to the hairline) will be assessed using the IGA.
11. **Lesion Count:** Lesion counts will be done by counting the number of facial open and closed comedones, pustules, papules and nodulo-cystic lesions from the jaw line to the hairline. All lesions will be counted, including those present on the nose.

12. **Application Site Reaction:** Subjects will be evaluated for any signs and symptoms such as erythema, dryness, burning/stinging, erosion, edema, pain and itching.
13. **Inclusion/Exclusion Criteria:** When the Subject has completed all screening procedures, compliance with the inclusion and exclusion criteria will be reviewed. After the inclusion and exclusion criteria have been confirmed, the Subject will be randomized to a treatment group. The Subject will be assigned a randomization number.
14. **Adverse Events:** The occurrence of all AEs will be assessed and documented following procedures.
15. **Randomization:** Subjects will be randomly assigned in [REDACTED] to receive the Test product or the Reference Product or the Placebo control, respectively. [REDACTED]
16. **Investigational Medicinal Product and Supplies:** The following will be dispensed during Visit 1 post randomization by the Independent Dispenser:

- The investigational product (1 pump)

- [REDACTED]
- [REDACTED]
- [REDACTED]
- [REDACTED]

Randomized Subjects will be instructed by the Independent Dispenser on the correct method for the application of the IMP. The application of the IMP will be performed by the Subject at home, instructed to apply the first dose in the evening. The study restrictions will also be reviewed with the Subject and an instruction sheet will be issued to the Subject.

Randomized Subjects will be provided with a diary and instructed how and when to complete the diary. They will be told that they are to document all treatments administered, including the date and time and all treatments missed. In addition, Subjects will be instructed to document all AEs. Subjects will also be instructed to call the study site if they experience any severe intolerability (i.e., local skin reactions) to IMP.

17. **Visit 2** (Day 28 [REDACTED] days from the date of Visit 1): will be scheduled and the Subject will be instructed to bring all IMP (used, unused, and partially used) and the Subject diary with him or her to this visit. Subjects will be reminded not to use any facial topical products within 12 hours prior to the next scheduled clinic visit.

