Subjects will return to the study site for Visit 2, Visit 3 and Visit 4. The Subject's concomitant medications (if any), IMP compliance and any AEs will be reviewed and documented. A temperature check and COVID-19 symptom (such as stuffy or runny nose, sore throat, shortness of breath (difficulty breathing), cough, low energy or tiredness, muscle or body aches, headache, chills or shivering, feeling hot or feverish (temperature check), vomiting, diarrhea, loss of sense of taste and smell) screening will be performed. A urine pregnancy test with a sensitivity of at least 25 mIU/ml hCG will be performed for female subjects of childbearing potential. A negative result of this test should be obtained.

The Subject will be evaluated for signs and symptoms of local irritation and any adverse events will be documented. The Subject's facial acne will be assessed using the IGA, the Subject's lesions will be counted, and these results will be documented.

If the Principal Investigator determines that the Subject's condition has worsened to the degree that it is unsafe for the Subject to continue in the study, the Subject may be discontinued from the study as a treatment failure and the Subject may be treated using the standard care or rescue medicines if there is exacerbation of their acne.

The subjects are instructed to bring their used IMP and their study diaries to each study visit.

Compliance with drug applications will be assessed at each visit. Additional pumps of IMP will be dispensed at the visit if required, and each Subject will receive new diaries during Visit 2 and Visit 3. In addition, all IMP and diaries will be collected from the Subject during each scheduled visit or the Early Discontinuation Visit.

At every study visit, all the procedures mentioned in the Table of events (Section 4) will be carried out. The treatment area of enrolled subjects will be assessed using IGA and lesion count. Additionally, adverse events (AEs) will be monitored, and the treatment area will be examined to assess application site reactions. Any change in concomitant medications will be noted.

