5.1.2 Exclusion Criteria

- 1) Female Subjects who are pregnant, lactating or planning to become pregnant during study participation.
- 2) Subjects with a history of hypersensitivity or allergy to trifarotene, tretinoin, retinoids, or any of the study medication ingredients.
- 3) Subjects with the presence of any skin condition that would interfere with the diagnosis or assessment of acne vulgaris (Such conditions include but are not limited to the following on the face: rosacea, dermatitis, psoriasis, squamous cell carcinoma, eczema, acneiform eruptions caused by medications, steroid or corticosteroid-induced acne, steroid folliculitis, or bacterial folliculitis, auto-immune disease, perioral dermatitis, carcinoid syndrome, mastocytosis, or acneiform eruptions caused by make-up and medication, facial psoriasis and facial eczema).
- 4) Subjects with nodulocystic acne (> 2 nodules and cysts). [Nodules or cysts defined as; deep-seated in the skin (i.e., centered in the dermis or subcutis) and an inflammatory lesion greater than or equal to 5 mm in diameter], acne conglobata, acne fulminans, secondary acne (chloracne, drug-induced acne, etc.), or acne vulgaris requiring systemic treatment.
- 5) Subjects with excessive facial hair (e.g., beards, sideburns, moustaches, etc.) that would interfere with diagnosis or assessment of acne vulgaris.
- 6) Subjects with tattoos or excessive facial scarring that, in the Investigator's opinion, may interfere with the evaluation of the subject's acne.
- 7) Subjects who have used within 6 months prior to screening/baseline oral retinoids (e.g., Accutane[®]) or therapeutic vitamin A supplements of greater than 10,000 units/day (multivitamins are allowed). These treatments with oral retinoids or Vitamin A supplements are prohibited during the study participation.
- 8) Subjects who have used within 1 month prior to screening/baseline neuromuscular blocking agents or androgen receptor blockers (e.g., spironolactone, Flutamide etc.).
- 9) Subjects who have had laser therapy, electrodesiccation, phototherapy and or cosmetic procedures (e.g., ClearLight[®] BOTOX, Filler, micro needling) to the facial area within 6 months prior to study entry.

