5.1.4 Precautions

The following precautions are to be taken during this study:

1. To minimize exposure to sunlight and or extreme weather conditions, a wide-brimmed hat or other protective clothing should be worn. 
2. The IMP should not be applied to cuts, open wounds, abrasions, sunburn or eczematous skin.
3. The IMP should not be applied to the eyes, the mouth/lips, the angles/corners of the nose or any mucous membranes.
4. Subjects should wash their hands before and after application of the product.

If a reaction suggesting sensitivity or chemical irritation occurs, the Principal Investigator should assess the Subject's condition as soon as possible (i.e., during an Unscheduled Visit) and determine whether treatment should be discontinued. If a Subject is discontinued from the study during an Unscheduled Visit, the Unscheduled Visit will be referred to as an Early Discontinuation Visit and all procedures scheduled for the Early Discontinuation Visit will be performed.

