6.3 Evaluation of Signs/Symptoms of Local Irritation/Application Site Reactions

At each study visit, beginning at Visit 1, Subjects will be evaluated for any signs and symptoms of local irritation such as erythema, dryness, burning/stinging, erosion, edema, pain and itching. The scores for each visit will be documented to allow a comparison between treatment groups.

The following scale will be used for the signs and symptoms of local irritation:

Score	Assessment	Description
0	Absent	None
1	Mild	Slight, barely perceptible
2	Moderate	Distinct presence
3	Severe	Marked, intense

Subjects with a screening/baseline irritation score of 3 (severe, marked/intense) will not be enrolled.

Signs and symptoms of local irritation are to be recorded only as AEs if they significantly worsen, require any medical intervention or result in subject discontinuation (eg. after screening/baseline, severe irritation (i.e., grade 3, described as severe or marked/intense) that requires treatment will be reported as an adverse event).

Local irritation reactions in the treatment area are common and the Investigator may instruct Subjects to stop the application of treatment (“rest period”) to reduce Subject discomfort and to allow local skin reactions to subside based upon the Investigator’s clinical assessment. The Investigator may advise the subject to use the Sponsor provided moisturizer at this time. Treatment should resume as soon as the reaction subsides sufficiently to allow reapplication. The [REDACTED]. The Subject should not modify or resume the treatment regimen without consultation with the Investigator. The Investigator may make this decision based upon a documented phone consultation or at an unscheduled visit. All dose modifications must be reported on the appropriate Study Medication Log & Dosing Compliance eCRF, along with Subject documenting in the subject diary.

The treatment period should not be extended beyond 12 weeks due to missed doses or rest periods. Subjects whose condition worsens or lesions do not respond to treatment following at least 28 days (or in the opinion of the Investigator) should be re-evaluated by the Investigator and management reconsidered.

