8.5 Unscheduled Visits and Early Discontinuation Visit

An Unscheduled Visit is allowed at any time, for any reason, if in the Principal Investigator's opinion, it is warranted. If the Unscheduled Visit is due to an AE, the Principal Investigator will determine whether additional visits are needed.

If a Subject is discontinued from the study during an Unscheduled Visit, the Unscheduled Visit will be referred to as an Early Discontinuation Visit and all procedures scheduled for the Early Discontinuation Visit will be performed. If the Unscheduled Visit is not an Early Discontinuation Visit (i.e., the Subject will continue to take part in the study), then the reason for the unscheduled visit is documented and required procedures at the discretion of Investigator considering the reason for visit will be performed apart from the collection of IMP and Subject diaries from Subjects.

If the Subject's condition has worsened to the degree that it is unsafe for the Subject to continue in the study, the Subject may be discontinued from the study as treatment failure and a standard of care treatment may be advised at the Principal Investigator's discretion.

[figure not shown]

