11 ADVERSE EVENTS

11.1 Recording of Adverse Events

An adverse event is any untoward medical occurrence in a Subject administered a medicinal product regardless of whether it has a causal relationship with this treatment. An adverse event can therefore be any unfavorable and unintended physical sign, symptom, or laboratory parameter that develops or worsens in severity during the course of this study, or significant worsening of the disease under study or of any concurrent disease, whether or not considered related to the medicinal product. A new condition or the worsening of a pre-existing condition will be considered an adverse event. Stable chronic conditions (such as arthritis) that are present before study entry and do not worsen during this study will not be considered adverse events.

Accordingly, an adverse event can include any of the following:

1. intercurrent illnesses
2. physical injuries
3. events possibly related to concomitant medication
4. significant worsening (change in nature, severity, or frequency) of the disease under study or other preexisting conditions
5. events occurring during diagnostic procedures or during any washout phase of this study
6. laboratory or diagnostic test abnormalities that result in the withdrawal of the patient from the study, are associated with clinical signs and symptoms or a serious adverse event, or require medical treatment or further diagnostic work up, or are considered by the investigator to be clinically significant (Note: Abnormal laboratory test results at the screening visit that preclude a patient from entering the study or receiving study treatment are not considered adverse events).
7. side effects caused by drug interaction.

The potential adverse reactions of TRIFAROTENE CREAM, 0.005% (Teva Pharmaceuticals, Inc.) are anticipated to be similar to those observed with the use of AKLIEF® (TRIFAROTENE 0.005% CREAM) (GALDERMA LABORATORIES, L.P., USA). The skin of certain sensitive individuals may become excessively red, edematous, swollen, blistered or crusted, local erythema, peeling at the site of application. Temporary hyper- or hypopigmentation has been reported with repeated application of tretinoin. **Trifarotene, like other retinoids, has been reported to cause severe irritation on eczematous skin and should be used with utmost**

caution in patients with this condition.

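### The visible call instruction to subjects covers only severe skin reactions, so a non-severe suspected sensitivity reaction may wait for the next visit

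*Protocol*

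**What the plan says.** Two provisions of the protocol deal with the same event from different sides.

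- **The subject's side.** Under 8.1 item 16, subjects are to be "instructed to call the study site if they experience any severe intolerability (i.e., local skin reactions) to IMP". In the readable text this is the only instruction that tells subjects to contact the site because of a symptom.
- **The investigator's side.** Section 5.1.4 states: "If a reaction suggesting sensitivity or chemical irritation occurs, the Principal Investigator should assess the Subject's condition as soon as possible". The assessment is to take place at an unscheduled visit and should settle whether treatment is discontinued. No minimum severity is attached.

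The surrounding text matters too. Section 6.3 says "Local irritation reactions in the treatment area are common and the Investigator may instruct Subjects to stop the application of treatment". It scores each sign from 0 to 3, with 3 as severe, marked or intense. Section 11.1 warns that "The skin of certain sensitive individuals may become excessively red, edematous, swollen, blistered or crusted". The SAP does not address when subjects should call.

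**The concern.** The investigator can make the prompt stop-or-continue decision in 5.1.4 only if the site hears of the reaction. The instruction that would bring it to the site's attention is narrower than the duty it serves, because reactions scoring 1 or 2 on the 6.3 scale fall below the call trigger.

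For ordinary retinoid irritation a severity threshold is sensible, since irritation is expected and the protocol manages it at visits and with rest periods. Suspected sensitivity is another matter. There the question is whether the subject should go on being exposed at all, and a low initial grade does not answer it. At stake is some avoidable continued exposure in a subject who may be reacting allergically. Nothing in the equivalence or superiority analyses depends on this point.

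**Working it through.** **Step 1: the routes by which the site could learn of a reaction between visits.** Take a subject who has a non-severe suspected sensitivity reaction, keeps applying and does not call.

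- *Call instruction (8.1 item 16).* Not triggered, because the reaction is not severe.
- *Diary.* Adverse events are written in it, but "all IMP and diaries will be collected from the Subject during each scheduled visit or the Early Discontinuation Visit" (section 3), so the site reads the entry at the visit.
- *Unscheduled visit.* "An Unscheduled Visit is allowed at any time, for any reason, if in the Principal Investigator's opinion, it is warranted" (8.5). The investigator must already know of the reaction to form that opinion.
- *Consultation under 6.3.* The subject may not modify or resume dosing without consulting the investigator. This prompts contact from someone who wants to change dosing. It does not reach someone who carries on as told.
- *Precaution 2 in 5.1.4, and 9.4.* Product must be kept off open wounds; 5.1.4 also names cuts, abrasions, sunburn and eczematous skin. A subject with broken or blistered skin would arguably have to withhold there, and so consult under 6.3. Swelling or a suspected allergic reaction on intact skin is not clearly covered.
- *Adverse event questioning (11.1).* It takes place at each contact, and the visit schedule in section 4 contains no contact between visits.

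None of these routes reliably alerts the site before the next visit in this case.

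**Step 2: the nominal wait.** Visits are on Days 0, 28, 56 and 84 (section 3).

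- Intervals: 28 − 0 = 28, 56 − 28 = 28 and 84 − 56 = 28 days.
- Onset just after the evening dose on a visit day: a wait of 28 days. Further applications fall on the evenings of days 1 to 27 of the interval, which makes 27.
- If the last evening's dose falls within the 12-hour period without topical products before the visit (8.1 item 17): 27 − 1 = 26 applications.
- As a share of the 84 planned daily doses: 26/84 = 0.310 and 27/84 = 0.321, or 31% to 32%.
- Onset before the evening dose on interval day 7: 28 − 7 = 21 days and 21 applications (20 if the last is omitted). On interval day 14: 28 − 14 = 14 days and 14 applications (13 if omitted).

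**Step 3: the redacted window.** Let the window be ±w days. The wait could reach 28 + w days from Visit 1 to Visit 2, and 28 + 2w days between later visits. Assuming w between 2 and 7 days, that is 28 + 2 = 30 to 28 + 7 = 35 days, and 28 + 4 = 32 to 28 + 14 = 42 days. The 28-day and 26-to-27-dose figures are therefore nominal worst cases and not strict upper bounds.

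**The case against.** The strongest reply is that the two provisions do not conflict. Section 5.1.4 tells the investigator what to do once a reaction is known. Section 8.1 gives subjects a minimum prompt, and nothing forbids a call about something milder. A reader might infer a contradiction, or that subjects are told not to report lesser reactions. The documents support neither. What remains is that the prompt is narrower than the duty.

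Second, the omission may be only apparent. The instruction sheet (8.1 item 16), the written study instructions (9.4) and the consent pages are not in the documents, and one sentence of 6.3 is redacted. Broader wording may exist there, so it cannot be said that subjects are never told to report milder reactions. This limits confidence but does not change what 8.1 says.

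Third, existing safeguards reduce the gap: precaution 2, the consultation rule, unscheduled visits for any reason, and discontinuation at the subject's wish after an adverse event (5.1.5 item g). Many subjects would also regard blistering or crusting on the face as severe and call under the present wording. All of this stands. It narrows the case to non-severe reactions, chiefly on intact skin, in a subject who continues.

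Fourth, exclusion criterion 2, "Subjects with a history of hypersensitivity or allergy to trifarotene, tretinoin, retinoids, or any of the study medication ingredients", might be read as setting a zero-severity threshold during treatment. It concerns history at entry and sets no threshold for contact on study. It shows at most that hypersensitivity is treated as a matter of its own, regardless of grade.

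Fifth, 5.1.4 also covers chemical irritation without a severity floor, and the proposed sentence does not extend to mild or moderate irritation. That is correct and deliberate.

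**Conclusion.** The point holds as a cheap patient-safety improvement of low severity, with medium confidence. Read literally, 8.1 item 16 can leave a non-severe suspected sensitivity reaction unassessed until the next scheduled visit, nominally up to 28 days, although 5.1.4 wants it seen as soon as possible.

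This rests on three conditions: the reaction is not severe, the subject keeps applying and does not call, and the unseen subject materials are no broader than 8.1. The documents give no frequency for such reactions, so no number of affected subjects can be estimated. The 31% to 32% of doses describes one worst-case subject and says nothing about how likely that case is.

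Two larger conclusions should be resisted. The text does not support the view that every irritation reaction should prompt a call, since 6.3 treats irritation as common and manages it clinically. Nor is there any effect on the efficacy analyses.

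**What to change.** Replace the last sentence of 8.1 item 16 with:

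> Subjects will also be instructed to call the study site promptly for any severe (marked or intense) local skin reaction, and for any swelling, blistering or crusting of the treated skin or any suspected allergic (sensitivity) reaction, even if not severe.

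The wording in brackets carries the 6.3 meaning of severe into plain language for subjects. Mild or moderate redness, dryness or burning/stinging without the added signs stays with scheduled visits under 6.3, so the change aligns 8.1 with the sensitivity part of 5.1.4 only.

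Then check that the subject's written instructions (9.4) and the instruction sheet say the same. If they already do, only 8.1 needs aligning. The cost is one sentence, that check, and some additional phone calls or unscheduled visits, which the protocol already permits.
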